## SYNOPSIS

Title:
A phase 1, open-label study to assess safety, biodistribution, and internal radiation dosimetry of  F-rhPSMA-7.3 injection in healthy volunteers, and to assess safety and investigate the imaging characteristics in subjects with prostate cancer
Sponsor:
Blue Earth Diagnostics Ireland Ltd.
Funding organisation:
Blue Earth Diagnostics Ltd.
Number of sites:
1
Background and Rationale:

The investigational medicinal product (IMP) of this clinical trial, F-rhPSMA-7.3 injection, is a promising PET ligand for the detection of prostate cancer (PCa). The F-rhPSMA-7 isomer mixture and the F-rhPSMA-7.3 stereoisomer have already been administered to humans under Section 13, Subsection 2b of the German Medicinal Products Act. Therefore, several hundred patients with PCa have been imaged clinically, which has helped to design the current study.
 
PCa is the most prevalent cancer of men and the third leading cause of death in industrialized countries. PCa is most commonly diagnosed in men aged >65 years. In its early stages it is largely asymptomatic and tumours are detected by identification of increased levels of prostate specific antigen (PSA) in peripheral blood. If detected early and when the disease is organ confined, the 5-year survival rate is approaching 100 %. However, increased PSA concentrations are also detected in benign conditions and for this reason additional testing is required to confirm the presence of cancer. Elevated PSA levels with no other explanation will often trigger a transrectal ultrasound-guided biopsy, which is an uncomfortable and invasive procedure. As the false positive rate of PSA screening is high, many men without PCa are referred for biopsy following PSA screening. The biopsy procedure, which is often not targeted based on imaging, may fail to detect significant cancerous foci; thus, treatment may be delayed to the detriment of the patient. Recently, multi-parametric magnetic resonance imaging (mpMRI) has gained diagnostic relevance and provided a non-invasive aid to help guide biopsy strategy. The recently published EAU-ESTRO-SIOG Guidelines on PCa recommend mpMRI in patients with negative biopsy when other test results are suspicious. However, mpMRI has limitations which include false negative rates of at least 10 % for intraprostatic lesions and poor performance for detection of small pelvic lymph node metastases. In addition, the natural history of PCa remains unclear, and distinguishing men who have an indolent cancer from those with a more aggressive cancer remains a clinical and research priority. These diagnostic challenges drive the demand for individualised staging of PCa that is both sensitive and specific. Accurate staging of newly diagnosed PCa aids the selection of an appropriate treatment strategy. Pelvic lymph node dissection at the time of radical prostatectomy can be used to clear lymph node metastases, and increasing evidence is available to support the use of PSMA PET as a decision-making aid for whether or not to perform this more extensive surgery. Similarly, the diagnosis of metastatic disease that lies outside of the field of surgery or


radiotherapy allows patients and clinicians to make more informed decisions about appropriate treatment, including potential metastasis-directed therapy.

PSMA (prostate-specific membrane antigen) is a 100 kD transmembrane glycoprotein that is overexpressed in nearly all prostate cancers, and less ubiquitously also in some other cancers such as breast cancer. Peptidomimetic glu-ureido-based PSMA inhibitors were initially described in 2001 (Kozikowski *et al.*, 2001), and bind to a carboxypeptidase active site in the extracellular domain of PSMA. In the last 5 years, many centres around the world have imaged PCa patients using PSMA-targeted PET tracers. Whilst initial results have demonstrated very promising diagnostic performance, no PSMA-targeted PET imaging agent has so far been licensed or approved, and availability is restricted to use under physicians' own responsibility and research protocols. Increasingly, the limited production capacity of the radiometal  $^{68}\text{Ga}$  represents a practical disadvantage when considering the high patient numbers that need to be imaged in this common disease. To overcome this,  $^{18}\text{F}$  labelled PSMA ligands have also been developed. This phase 1 study aims to evaluate the safety, biodistribution, optimal administered radioactivity and imaging time post administration for PCa lesion visualisation of an  $^{18}\text{F}$  labelled radiohybrid (rh) PSMA ligand.

**Study design:**

This is a phase 1, open-label study to assess the safety, biodistribution, and internal radiation dosimetry of  $^{18}\text{F}$ -rhPSMA-7.3 injection in healthy volunteers, to assess its safety in patient volunteers with PCa and to obtain data to optimise the imaging protocol for future studies in subjects with PCa.

**Primary objective:**

To assess the safety of a single administration of  $^{18}\text{F}$ -rhPSMA-7.3 in healthy subjects and subjects with PCa.

**Secondary Objectives:**

1. To determine the biodistribution of  $^{18}\text{F}$  following intravenous (i.v.) administration of  $^{18}\text{F}$ -rhPSMA-7.3 and hence calculate the internal radiation dosimetry and the effective dose (ED) in healthy volunteers.
2. To explore the optimisation of PET imaging with  $^{18}\text{F}$ -rhPSMA-7.3 injection in visualizing tumours in subjects with biopsy-proven PCa.
3. To perform kinetic modelling on the distribution of  $^{18}\text{F}$ -rhPSMA-7.3 in subjects with PCa.
4. To use the kinetic modelling data to optimise the imaging protocol for future studies in subjects with PCa.
5. To determine the *in vivo* stability of  $^{18}\text{F}$ -rhPSMA-7.3 injection by determining proportion of radioactive parent compound present over time.

**Number of subjects:**

6 evaluable healthy volunteer subjects (3 males and 3 females) followed by 9 evaluable patients (3 in each patient cohort) with PCa at a single centre.

**Subject selection criteria:****Healthy Volunteers (3 males, 3 females)****INCLUSION CRITERIA (Healthy Volunteers)**

1. The subject is between 21 and 65 years old.
2. The subject is willing to abstain from sexual intercourse for 24 hours after IMP administration.
3. The male subject is willing to practice effective contraception for 3 months after IMP administration.

4. The female subject is post-menopausal or surgically sterile.
5. The subject is able and willing to provide signed, dated and timed informed consent to comply with study procedures, before any study-related procedure is performed.
6. The subject has normal or clinically acceptable medical history, physical examination, and vital signs findings during the screening period (up to 21 days before administration of study drug) as determined by the investigator.
7. The subject's ECG and clinical laboratory test results are within normal limits, or if any are outside of normal limits, they are considered to be clinically insignificant, as determined by the investigator.
8. The subject has negative test results for drugs of abuse and alcohol at screening and on the day of IMP administration/PET imaging.
9. The subject's body mass index is <30 kg/m^2 and body weight is <90 kg.

**EXCLUSION CRITERIA (Healthy Volunteers)**

1. The subject has been previously included in this study and has received any dose of the study medication.
2. The subject has received, or is scheduled to receive, another IMP from 3 months before to 1 week after administration of F-rhPSMA-7.3.
3. The subject has received ionising radiation exposure from clinical trials or medical examinations or treatment (other than plain radiographs of the chest or bones, or comparable) in the last 12 months.
4. The subject is undergoing monitoring of occupational ionising radiation exposure.
5. The subject suffers from claustrophobia.
6. The subject has bilateral hip prostheses.
7. The subject has tested positive for hepatitis B, hepatitis C, or human immunodeficiency virus.
8. The subject has a history of alcohol or drug abuse within the previous 12 months, or is a habitual user of excessive amounts of alcohol (>21 units per week).

**Patients with Prostate Cancer****INCLUSION CRITERIA (All Cohorts)**

1. The subject is a male and is 18-80 years old.
2. The subject has histologically confirmed adenocarcinoma of the prostate without neuroendocrine differentiation or small cell features.
3. The subject is willing to abstain from sexual intercourse for 24 hours after IMP administration and to practice effective contraception for 3 months after IMP administration.
4. The subject is able and willing to provide signed, dated and timed informed consent to comply with study procedures, before any study-related procedure is performed.
5. The subject has clinically acceptable medical history, physical examination, and vital signs findings during the screening period, as determined by the investigator (up to 21 days before administration of study drug), apart from findings related to PCa.
6. The subject's ECG and clinical laboratory tests are within normal limits, apart from findings related to PCa, or if any are outside of normal limits, the out-of-range values are considered to be not clinically significant as determined by the investigator.

7. Eastern Cooperative Oncology Group [ECOG] performance status 0-2 (Appendix 2).

**Cohort A specific inclusion criteria – High risk primary PCa**

8. Unfavourable intermediate-risk or high-risk PCa as defined by NCCN Guidelines Version 2.2019 (clinical stage  $\geq$ T2b or PSA  $>10$  ng/mL or Gleason score  $\geq 4 + 3 = 7$ ).

9. Scheduled for radical prostatectomy with or without pelvic lymph node dissection.

**Cohort B specific inclusion criteria - Hormone sensitive metastatic PCa**

10. Castration naïve metastatic PCa with a known number of metastases or a high likelihood of lymph node metastases and/or bone metastases.

11. Either clearly demonstrated disease by site standard of care imaging performed as part of the subject's routine clinical work-up within 12 weeks before enrolment or biochemical recurrence with a PSA  $< 15$  ng/mL.

**Cohort C specific inclusion criteria – Castration resistant metastatic disease**

12. A quantifiable number or a high likelihood of metastases documented by standard of care imaging performed as part of the subject's routine clinical work-up within 12 weeks before enrolment or by biochemical progression (see 14a).

13. Ongoing androgen deprivation with luteinizing hormone-releasing hormone (LHRH) agonist/antagonist therapy or bilateral orchiectomy.

14. Castrate serum testosterone  $< 50$  ng/dL or 1.7 nmol/L plus either;

- a. Biochemical progression: Three consecutive rises in PSA at least one week apart resulting in two 50 % increases over the nadir, and a PSA  $> 2$  ng/mL or,
- b. Radiological progression: The appearance of new lesions (either two or more new bone lesions on bone scan or soft tissue lesion(s) progression using RECIST (Response Evaluation Criteria in Solid Tumours)).

**EXCLUSION CRITERIA (All patient Cohorts)**

1. A biopsy has been obtained from the prostate within the 28 days before enrolment.
2. Patients with extensive metastatic disease (more than 20 lesions).
3. Patients with a second primary cancer or any other underlying disease which might confound interpretation of the study results.
4. The subject has had any major surgery within 2 months prior to screening.
5. The subject has bilateral hip prostheses.
6. The subject has received, or is scheduled to receive,  $^{68}\text{Ga}$ -PSMA-11 or  $^{18}\text{F}$ -PSMA-1007 from 1 month before to 1 week after administration of  $^{18}\text{F}$ -rhPSMA-7.3, or any other IMP from 3 months before to 1 week after administration of  $^{18}\text{F}$ -rhPSMA-7.3.
7. The subject has a history of alcohol or drug abuse within the previous 12 months, based on a review of medical records or other available evidence.
8. The subject has known hypersensitivity to  $^{18}\text{F}$ -rhPSMA-7.3 injection or any of its constituents.
9. Subjects administered any high energy ( $>300$  keV) gamma-emitting radioisotope within five physical half-lives, or any intravenous iodinated contrast medium within 24 hours, or any high density oral contrast medium (oral water contrast is acceptable) within 5 days prior to study drug administration.

10. Subjects who have recently received an x-ray contrast agent (<24 hr for i.v. agents and <5 days for oral agents).
11. Subjects with a history of claustrophobia or panic attacks when in confined spaces.

**Cohort A and B specific exclusion criteria**

12. The subject is being treated or has been treated for PCa with chemotherapy or radiation therapy.
13. Patients currently receiving or with a prior history of hormonal treatment/androgen deprivation therapy including bilateral orchiectomy.

**Cohort C specific exclusion criteria**

14. Radiation therapy for treatment of any metastatic lesions in the field of view of the dynamic images.

**Test product, administered activity and route of administration:**

F-rhPSMA-7.3 Injection. Approximately 225 MBq ( $\pm 10\%$ ) for healthy volunteers, single i.v. injection (the total radiation effective dose will not exceed 10 mSv).

For subjects with PCa, the administered radioactive dose will be based upon the results of the preliminary dosimetry analysis on data from the healthy volunteer subjects. The total radiation effective dose will be 9.2 mSv); 300 MBq ( $\pm 10\%$ ) will be injected.

The total maximum dose for both healthy volunteers and patients will be less than 100  $\mu$ g.

**Control product, dose and route of administration:**

Not applicable.

**Trial design, duration of subject participation and duration of study:**

A phase 1, open label, single administration, healthy volunteer and patient study for a PET imaging agent.

Each subject will receive a single administration of F-rhPSMA-7.3 by i.v. injection which will be immediately followed by a PET-CT scan.

[figure not shown]
**Standard of Truth (Cohort A only):**

Histopathological diagnosis in patients undergoing radical prostatectomy. PSMA immunohistochemistry will be employed for exploratory analysis of Cohort A prostate specimens removed at surgery.

**Duration of Subject participation:**

[figure not shown]
Up to 52 days (screening period of up to 21 days, IMP administration visit, 24-hour follow-up visit and 30-day follow-up by telephone; additional visits will be scheduled as needed in case of AEs).

**Image Acquisition****Healthy Volunteers**

The healthy volunteers will undergo 3 CT attenuation-correction scans, each followed by whole-body (WB) PET acquisitions; the PET acquisitions will be obtained at scheduled time points up to 4 hours post injection (p.i.) for biodistribution and radiation dosimetry assessments.

### **Subjects with Prostate Cancer**

The subjects with PCa will undergo two CT attenuation-correction scans and dynamic PET imaging of the pelvic region (Cohort A; BCR patients in Cohort B; patients with biochemical progression in Cohort C) or the body region(s) with one or more metastases defined as representative target lesions (metastatic patients in Cohort B and radiologically progressive patients in Cohort C) for 45 min, then 15 min break, and then two base of skull to proximal-thigh acquisitions up to 118 mins p.i.

### **Efficacy, Pharmacokinetic and Safety Variables:**

#### Efficacy:

- Standardised uptake values (SUV) (e.g. SUVmax, SUVmean, SUVR)
- Uptake irreversibility/reversibility
- Lesion detectability: comparison of SUV in detected lesion(s) against pathology grading.

#### Pharmacokinetics:

- Time-activity curves.
- F radioactivity concentration assays in whole blood and plasma.
- % radioactive parent compound present over time, and proportions of possible radioactive metabolites, if found in measurable amounts in the radio-HPLC analysis.
- Radioactivity in urine.

#### Safety:

- AEs
- Clinical laboratory parameters (serum biochemistry including liver function tests, haematology, coagulation/clotting and urinalysis)
- Vital signs
- ECG (Electrocardiography)
- Physical examination findings
- Injection site monitoring.

**Statistical Methods and Planned Analysis:****Healthy Volunteer Evaluability Criteria:**

A healthy volunteer is considered as evaluable for efficacy when he/she completes scanning sessions I, II and III, and collection of venous blood and urine analysis (as described in the Study Imaging Manual) to be able to undertake a calculation of the subject's internal radiation dosimetry. As it is important that the study has the required number of evaluable healthy volunteers, these evaluability criteria will be applied, and if the healthy volunteer is not evaluable, an additional subject may be included in the study to substitute for the non-evaluable subject.

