**Radiation Dosimetry Data:**

Quantitative measurements of F radioactivity in volumes of interest (VOIs) from whole-body healthy volunteer images over target organs will be made at several time points p.i. Time activity curves will be generated and integrated to calculate the cumulated radioactivity in each organ. OLINDA/EXM (or similar software) provides a means of calculating the radiation absorbed doses associated with the internal distribution of a radioactive substance using the Medical Internal Radiation Dose (MIRD) schema and requires, as input, the normalised cumulated activities (also known as residence times) for source organs, tissues and contents. The normalised cumulated activity is the cumulated activity per unit administered activity. The cumulated activities are then used with the OLINDA/EXM software to calculate the ensemble of organ-absorbed doses to the MIRD target organs in an adult phantom from which the effective dose can be evaluated. A dynamic urinary bladder model is used and the internal radiation dosimetry is calculated for 1-hour and 3.5-hour urinary bladder voiding intervals. The effects of the

urinary bladder voiding interval upon the urinary bladder wall dose and the effective dose will also be evaluated. Descriptive statistics of absorbed doses to target organs and tissues specified in the MIRD schema will be tabulated.

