#### 4.10 Evaluability criteria and additional subjects

Healthy Volunteer Evaluability Criteria:

As it is important that the study has the required number of evaluable healthy volunteers, the following criteria will be applied, and if the healthy volunteer is not evaluable for efficacy, an additional subject may be included in the study to substitute for the non-evaluable subject:

- Completion of scanning sessions I, II and III and collection of venous blood and urine analysis (as described in the Study Imaging Manual) to be able to undertake a calculation of the subject's internal radiation dosimetry.

Patient Evaluability Criteria:

As it is important that each cohort has the required number of evaluable patients, the following criteria will be applied and if the patient is not evaluable for efficacy, an additional subject may be included in the study to substitute for the non-evaluable subject:

- Completion of scanning sessions I and II and collection of venous blood and urine analysis (as described in the Study Imaging Manual) to be able to perform kinetic modelling.
- At least one positive lesion on the F-rhPSMA-7.3 scan.
- Cohort A only: Radical prostatectomy performed within 30 days of the F-rhPSMA-7.3 scan. In case of a delay of the planned surgery by up to 2 days beyond this 30-day window, a subject may still be considered evaluable.

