#### Healthy Volunteers

Blood samples should be collected at the following time-points as calculated from the time of  $^{18}\text{F}$ -rhPSMA-7.3 administration: 30 sec, 60 sec, 90 sec, 4 min 30 sec, 5 min, 6 min, 7 min, 8 min, 15 min, 31 min, 47 min, 75 min, 120 min, 180 min, and 250 min after injection. Sample volume is 2 ml except at the 5, 8, 15, 31, and 47 min time points when an extra 5 ml sample is collected for radioactive metabolite analysis.

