#### 8.2.3 Data sets to be analyzed

The safety analysis set (SAF) will include all subjects who received any administration of the IMP.

Evaluable Analysis set (EAS) will include subjects who met all inclusion and exclusion criteria, received IMP, underwent PET/CT scans and met the scan evaluability criteria set out in section 4.10.

Statistical analyses for the primary and secondary endpoints (besides safety) will be performed using EAS. Safety will be assessed using the safety analysis set (SAF).

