## 8.2.8 Analysis of radiation dosimetry data

Quantitative measurements of F radioactivity in volumes of interest (VOIs) from whole-body healthy volunteer images over target organs will be made at several time points p.i. Time activity curves will be generated and integrated to calculate the cumulated radioactivity in each organ. OLINDA/EXM provides a means of calculating the radiation absorbed doses associated with the internal distribution of a radioactive substance using the Medical Internal Radiation Dose (MIRD) schema and requires, as input, the normalised cumulated activities (also known as residence times) for source organs, tissues and contents. The normalised cumulated activity is the cumulated activity per unit of administered radioactivity. The cumulated activities are then used with the OLINDA/EXM software to calculate the ensemble of organ-absorbed doses to the MIRD target organs in an adult phantom from which the effective dose can be evaluated. A dynamic urinary bladder model is used and the internal radiation dosimetry is calculated for 1-hour and 3.5-hour urinary bladder voiding intervals. The effects of the voiding interval upon the urinary bladder wall dose and the effective dose will also be evaluated. Descriptive statistics of absorbed doses to target organs and tissues specified in the MIRD schema will be tabulated.

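### Volunteers' parent-fraction analysis is tied to late dosimetry scans it does not use, because one evaluable set serves every non-safety endpoint

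*Protocol*

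**What the plan says.** The synopsis (Healthy Volunteer Evaluability Criteria) and section 4.10 set the same joint rule. In the synopsis a volunteer is evaluable when he or she "completes scanning sessions I, II and III, and collection of venous blood and urine analysis". In section 4.10 it reads "Completion of scanning sessions I, II and III and collection of venous blood and urine analysis". The stated purpose is "to be able to undertake a calculation of the subject's internal radiation dosimetry"; in vivo stability is not mentioned.

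Section 8.2.3 admits to the EAS only subjects who, among other conditions, "met the scan evaluability criteria set out in section 4.10". It then states: "Statistical analyses for the primary and secondary endpoints (besides safety) will be performed using EAS". It defines no set for any particular endpoint.

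Secondary endpoint 5 (section 2.4) is the percentage of radioactive parent compound in plasma over time, in volunteers as well as patients. Section 7.4.1 gives the volunteers' sampling scheme: 2 ml at each time point, "except at the 5, 8, 15, 31, and 47 min time points when an extra 5 ml sample is collected" for metabolite analysis. Section 6.2 lists the minimum volunteer scanning data as 1 to 90 min, 150 to 178 min and 220 to 248 min.

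**The concern.** A completeness rule written for dosimetry decides who enters an analysis that uses only early blood samples. Dosimetry plausibly needs all three scanning sessions, since activity is measured on "whole-body healthy volunteer images over target organs will be made at several time points p.i" and the time-activity curves are then integrated. The parent fraction does not need them.

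A volunteer who cannot go through with the second or third session has already given every parent sample, yet falls outside the set in which parent fraction is analysed. At stake is one subject's complete stability profile in a group of six, a size that section 8.1 describes as the smallest informative number.

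**Working it through.** **Planned number.** Section 8.1 gives 3 males + 3 females = 6 evaluable volunteers, and 6 + 9 = 15 subjects in all. Both sums are right. The protocol states no alpha, power, SD or dropout rate, so there is no sample-size calculation to reproduce.

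**Timing.** I take sessions I, II and III to be the three windows in section 6.2.

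| Item | Minutes after injection |
|---|---|
| Parent/metabolite samples (7.4.1; Table 2, note e) | 5, 8, 15, 31, 47 |
| Session I | 1 to 90 |
| Session II | 150 to 178 |
| Session III | 220 to 248 |

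- Last parent sample to start of session II: 150 − 47 = 103 min.
- Last parent sample to start of session III: 220 − 47 = 173 min.
- Parent samples lost by missing session II or III: 0 of 5.
- Of the 15 scheduled radioactivity samples, 12 fall by 90 min, 13 before 150 min and 14 before 220 min. Most of the blood curve therefore also precedes the late scans, though not all of it.

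**Chain of rules.** Missed session II or III → section 4.10 not met → not in the EAS (8.2.3) → not in the analysis of endpoint 5 (8.2.3). No step refers to the blood samples.

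**Effect on precision.** The standard error of a mean is SD/√n, with the SD taken as unchanged.

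- No substitute: n = 5 instead of 6. Ratio √(6/5) = 1.095, about 10% larger.
- Substitute enrolled: n = 6 under the present rule, 7 if both volunteers were used. Ratio √(6/7) = 0.926, so about 7% of standard error is forgone.
- As 95% t half-widths, t(0.975, n−1)/√n, in SD units: n = 5, 1.242; n = 6, 1.049; n = 7, 0.925. Thus 5 against 6 is 1.242/1.049 = 1.18 (18% wider), and 7 against 6 is 0.925/1.049 = 0.88 (12% narrower). These are only a yardstick, since the protocol plans no confidence intervals.

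The two cases are alternatives and cannot be added together.

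**How often.** The protocol gives no rate of missed scans. If each volunteer independently misses a late scan with probability f, the chance that at least one of six does so is 1 − (1 − f)^6. For assumed f of 2%, 5%, 10% and 15% this gives 11%, 26%, 47% and 62%.

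**The case against.** The strongest reply is that nothing is really lost. Section 8.2.4 says that collected data are in general summarised and listed, and section 4.9 keeps withdrawn subjects' data as study data. A substitute may be enrolled, which restores six. The study is exploratory with no hypotheses (8.2.2), so no test result is at risk. Much of this stands: the data would not be destroyed, the loss is conditional on a missed scan, and its frequency is unknown. But section 8.2.4 is a general statement, whereas section 8.2.3 is the specific rule for the secondary endpoints. If the general statement were meant to prevail, the N for endpoint 5 would be ambiguous, which also calls for a clarification.

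Three stronger readings are tempting and not supported.

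- *Dosimetry needs no venous blood, so requiring it is an error.* Section 8.2.8 names image volumes and a bladder model and does not mention blood, but it does not say these are the only inputs. The evaluability rule ties blood to the dosimetry calculation through the Study Imaging Manual, which is not among the documents. Secondary endpoint 1 itself includes activity in whole blood and plasma.
- *A substitute would be irradiated to replace data that already exist.* A volunteer who misses a late scan lacks scanning data that section 6.2 lists as the minimum. A substitute would supply missing dosimetry, and substitution is permitted rather than required.
- *Precision within one sex collapses.* The protocol specifies no dosimetry or stability analysis by sex, so interval widths for three or two subjects describe nothing planned.

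**Conclusion.** The point holds in a narrow form. As section 8.2.3 is written, a dosed volunteer who misses session II or III leaves the analysis of percent parent in plasma although all five samples were taken at least 103 min before the missed scan began. The cost is one subject: a standard error about 10% larger if there is no substitute, or an unused valid seventh subject if there is one.

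This rests on a literal reading of section 8.2.3, on matching the three sessions to the windows in section 6.2, and on an unchanged SD. It does not depend on the SAP, because the protocol itself fixes the analysis set. The harm is lost information on a descriptive endpoint; it is not bias in a test, and no excess radiation exposure is shown.

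**What to change.** In section 8.2.3, state that the blood, plasma and parent-fraction endpoints in healthy volunteers are analysed in all dosed volunteers who have the samples needed for the analysis concerned, whatever scans were completed. Keep the EAS for dosimetry. The phrase on needed samples matters because summaries that use the latest blood draws could still lack data from a volunteer who leaves early.

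The evaluability and substitution rules in the synopsis and section 4.10 need not change for this. Separately, check against the Imaging Manual and secondary endpoint 1 whether, and how completely, venous blood is required for dosimetry evaluability.

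The cost is a sentence in one section and one further analysis set. N may differ between endpoint tables, so each table should state its own N.
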